10.2. HAE Medical and Medication History

An HAE medical history questionnaire provided by the sponsor will be completed at screening. All questions should be completed by the investigator (or designee) from historical source documentation when available, with P/C or subject input as necessary to complete the remaining questions. The completed HAE Medical History Questionnaire will be considered a source document and must be entered in the CRF.

10.3. Physical Examination

A full physical examination will be conducted at screening, baseline (Day 1), and at Week 12 (beginning of Part 2). Targeted or symptom-directed examinations will be performed only as necessary at all other visits.

Genitourinary and breast examinations may be omitted when not required by normal site practice. With female subjects past the age of menarche, the age of menarche should be determined.

10.4. Weight/Height/Body Mass Index

Subject weight is important for this study as the dose of berotralstat will be based on subject weight. Therefore, the site should be diligent in accurately taking and recording subject weight. Subjects should be weighed in light clothing with shoes and other heavier items (eg, belts or phones) removed. Heavier outer clothing (eg, jackets or sweaters) should also be removed.

Height should be recorded at the indicated visits. Body mass index (BMI) should be calculated at all visits where weight and height are measured using the following formula:

$$\text{BMI} = \text{weight (kg)} / \text{height (m)}^2$$

10.5. 12-lead Electrocardiograms

A standard bedside or routine 12-lead ECG machine that calculates heart rate and measures the PR, QRS, QT, RR, and QTc intervals will be used. Prior to obtaining an ECG, subjects should rest quietly for at least 10 minutes. Resting may be in a supine position or other position (eg, on the P/C's lap) as age appropriate for the subject.

Qualified site personnel should review the ECGs and automated findings in real time for gross abnormalities and interval measurements of concern (absolute readings and for post-baseline ECGs, a change from baseline). For all ECGs, the clinical interpretation of the ECG and calculated QTc should be recorded directly on a hard copy of the ECGs. Copies of the ECGs may be requested by the sponsor. All subject identifiers will be masked prior to provision to the sponsor.

Baseline (pre-dose) ECGs will be obtained in triplicate (ie, 3 separate readings taken at 1- to 5-minute intervals) with baseline values calculated from an average of the 3 readings. All other ECGs will be single assessments.

An ECG should be repeated for a change from baseline in QTc > 60 msec or a QTc interval > 500 msec.

If AEs commonly associated with prolonged QTc interval (eg, unexplained intermittent or continuous lightheadedness, syncope, palpitation, chest pain) are reported or the dose is modified, additional ECGs should be recorded. ECGs obtained due to dose modification should be taken approximately 2 to 6 weeks after dose modification and should be aligned with PK blood sample timelines described in Section 10.9.1 to the extent possible.

10.6. Vital Signs

Blood pressure (systolic and diastolic) and pulse rate should be taken after the subject has rested in the supine position for at least 5 minutes. For younger subjects who cannot rest for 5 minutes in a supine position, sitting quietly on the P/C's lap is an acceptable alternative. Blood pressure measurements must be obtained with an age-appropriate cuff size and with the subject's arm supported at the level of the heart. It is acceptable to obtain a pulse rate from the blood pressure or ECG machine. Respiratory rate will be captured at screening, baseline, and Week 12 (beginning of Part 2) only.

10.7. Clinical Laboratory Evaluations

Blood samples will be obtained per the schedule of events. Numbing options (eg, numbing cream or ice spray) may be used per site standard practice. Blood sample volume limits should not exceed 3% of the total blood volume during a period of 4 weeks and should not exceed 1% at any single time ([European Commission 2008](#)). Further details and guidance on maximum blood draws will be provided in the laboratory manual. Urine samples will be collected from all children old enough to provide a reasonable clean-catch sample. If very young children are not able to provide a urine sample, the lack of a sample should be noted in the source documents; lack of sample collection in small children will not be considered a protocol deviation. Individual laboratory tests to be performed are provided in [Table 3](#).

All laboratory samples will be collected using kit supplies provided by the central laboratory, which will also analyze all samples. The use of a local laboratory is permitted in specific circumstances with the permission of the sponsor medical monitor. If any results are obtained from both central and local laboratories for the same assessments at a single study time point, only the central laboratory results will be used for study purposes. A laboratory reference manual will be provided to the site detailing kit contents, reordering instructions, sample collection, handling, storage, and shipment.

Results from the laboratory values should be reviewed as received by the investigator. Evidence of this review should be provided in the source records and may include printing of the laboratory reports with a signature attesting to a review. For out-of-range laboratory findings, the interpretation of clinically significant or not clinically significant should be denoted in the source records. Clinically significant laboratory findings in the opinion of the investigator should be recorded as an AE and handled as described in [Section 11](#).

Table 3: Clinical Laboratory Evaluations

Chemistry	Coagulation

 • Albumin • Alkaline phosphatase (ALP) • Alanine aminotransferase (ALT) • Aspartate aminotransferase (AST) • Bilirubin (total and direct) • Blood glucose • Blood urea nitrogen (BUN) • Electrolytes (calcium, sodium, potassium, chloride, bicarbonate [CO₂], phosphorus) • Lipid panel (total cholesterol, triglycerides) • Creatine kinase • Creatinine and calculated creatine clearance (CL_{CR}) • Gamma-glutamyl transferase (GGT) • Lactate dehydrogenase (LDH) • Total serum protein • Uric acid • If amylase is > 2 × upper limit of normal (ULN), reflex to lipase 	
 • Prothrombin time (PT) and international normalized ratio (INR) • Activated partial thromboplastin time (aPTT)
	Pregnancy Test
	Only for girls who have begun to menstruate: Serum (screening) and urine (other specified visits) beta-human chorionic gonadotropin (βHCG) for girls of childbearing potential only ^a
	Hematology
Urinalysis 
 • Specific gravity • Blood • Bilirubin • Glucose • Leukocytes • Ketones • Nitrites • pH • Protein • Urobilinogen • Microalbumin to creatinine ratio • Reflex microscopy if dipstick is abnormal 	
 • Hemoglobin • Hematocrit • Erythrocytes • Mean corpuscular hemoglobin (MCH) • Mean corpuscular hemoglobin concentration (MCHC) • Mean corpuscular volume (MCV) • White blood cell count, with differential (lymphocytes, monocytes, neutrophils, eosinophils, and basophils) • Platelets
	Additional Tests
	
 • C1 esterase inhibitor (C1-INH) level and function^b • C4^b • SERPING-1 analysis^b

^a A serum pregnancy test should immediately be drawn and sent for analysis for any positive urine pregnancy test.

^b Only if required to confirm HAE diagnosis.

CL_{CR} will be calculated using the Modified Schwartz formula and actual body weight as shown in the laboratory manual.

10.8. Confirmation of HAE Diagnosis

Subjects must have confirmed HAE to be eligible for study participation. Several methods may be used to confirm an HAE diagnosis.

- C1-INH functional level and C4 level: If necessary to satisfy eligibility criteria, blood samples for C1-INH functional level and C4 will be drawn at the screening visit; samples should not be drawn within 3 days of C1-INH administration (eg, use for treatment of an HAE attack).
 - Immunogenic C1-INH antigenic level results below the LLN or functional C1-INH results < 50%, and a C4 level below the LLN reference range.
 - For subjects with C1-INH function $\geq 50\%$ but less than the assay LLN, a SERPING-1 gene mutation known or likely to be associated with HAE Type I or II, as assessed during the screening period OR a repeat C1-INH functional level < 50% will be considered acceptable for enrollment
- Laboratory documentation of historical C1-INH functional level below the assay LLN.
- Historical or new laboratory documentation of a SERPING-1 mutation known or likely to be associated with HAE.
- For subjects currently receiving C1-INH based prophylactic therapies, a confirmed family history of C1-INH deficiency. The investigator should document this based on either the investigator's personal knowledge (ie, if a relative of the screening subject is also a patient of the same investigator/practice) or interaction with medical staff of the treatment facility where the relative receives HAE care, who confirms the diagnosis. No historical laboratory documentation on the relative should be collected in the source documents.

10.9. Pharmacokinetics

All plasma samples for determination of berotralstat will be analyzed using a validated liquid chromatography-mass spectrometry assay.

Blood samples for analysis of PK parameters will be drawn on all subjects as indicated in the Schedule of Assessments. At the Week 2 visit, a series of samples will be collected for PK analysis to allow for determination of PK parameters including C_{max}.

Actual date and time of sample collection will be recorded in the CRF. Sites will ensure that the time of the dose of berotralstat taken prior to the blood draw is recorded in the source documents and CRF. Sites should communicate to the P/C the importance of providing the most accurate time of dosing prior to the PK sample collection.

Instructions for collection, processing, storage, and shipment of PK samples will be provided to the clinical site in a separate document.

In Cohorts 1, 2, and 3, at the Week 2 study visit where multiple PK samples are to be collected, plasma samples for PK analysis should be collected pre-dose and at 1 ± 0.5 , 2 ± 0.5 , 4 ± 1 , and 6 ± 1 hours post dose (exact timing of the dose and each blood draw must be recorded). In Cohort 4, plasma samples for PK analysis should be collected pre-dose, 1 to 2 hours post dose, and 4 to 6 hours post dose. PK samples should be collected as close to the nominal collection timepoint as possible, but all scheduled PK samples should be collected even if they are outside the sampling window. The date and time of the PK blood draws and the last dose of berotralstat taken prior to the blood draw will be captured in the CRF. Of note, in younger and/or smaller subjects, the number of samples and/or volume of blood drawn for each sample may be reduced to ensure volumes collected fall within acceptable ranges. If plasma samples for PK analysis cannot be collected as described above at Week 2, sites are required to document the reason in source notes and collect samples for PK analysis prior to or during the Week 6 visit.

A single plasma PK sample is to be collected at Weeks 12, 24, 36, and 48. Additional plasma PK samples may be collected during the study if prescribed by the principal investigator as indicated for clinical management of the subject or if a previously scheduled sample was not collected and/or evaluable. The date and time of the PK blood draw, the last dose of berotralstat taken prior to the blood draw, and if the dose was taken with food will be captured in the CRF. As noted above, accuracy of the previous dose time of berotralstat is important.

PK sample collection may be discontinued following the interim data cut used to finalize the population PK model and pharmacometric analysis report, at the discretion of the sponsor.

10.9.1. Plasma Pharmacokinetic Samples for Dose Modifications

Adjustments to the berotralstat dose may be required during the study based on safety and/or PK findings. If the berotralstat dose is adjusted due to an AE or high exposure level, the subject will be required to provide blood samples for analysis of PK parameters as follows:

- Subjects in Cohorts 1 and 2 will provide a PK sample 20 to 24 hours after their previous dose of berotralstat, and another sample 2 to 4 hours after taking their daily dose of berotralstat.
- Subjects in Cohorts 3 and 4 will provide a PK sample 20 to 24 hours after their previous dose and, if possible, another sample at 2 to 4 hours after taking their daily dose of berotralstat.

These samples will be collected approximately 2 to 6 weeks after the dose adjustment. If a telephone call or telemedicine appointment is scheduled for the next visit, an in-person clinic visit may be conducted instead. Note: home health collection may be an option if available per country requirements.

Subjects with dose adjustment will be asked to take their daily dose in the morning for a minimum of 2 weeks before the PK draw will be completed. On the day of PK draw, subjects should take their daily dose during the visit with food.

The date and time of berotralstat dosing and PK sample collection, as well as whether the dose was taken with food, will be recorded in the source documents and the CRF.

Subjects with dose adjustments based on weight in Part 2 or Part 3 of the study should provide PK samples approximately 2 to 6 weeks after the dose adjustment, as described in the bulleted

list above. If samples cannot be collected in this timeframe, they must be collected at the next visit.

PK sample collection may be discontinued following the interim data cut used to finalize the population PK model and pharmacometric analysis report, at the discretion of the sponsor.

10.10. Adverse Events

AEs will be assessed and recorded from the time that the informed consent form (ICF) is signed through the last follow-up visit or until the AE is resolved or the subject is in a clinically stable condition with regard to the AE. Full details on recording and reporting AEs are provided in Section [11.1.1.4](#).

10.11. HAE Attack Diary

The sponsor will supply paper diaries to sites to be distributed to the P/C for recording the subject's HAE attacks. The P/C will fill out the HAE attack diary whenever an attack (or suspected attack) occurs. If the subject reports an attack or if the P/C suspects that an attack has occurred, additional details should be entered into the diary including start and stop time of the attack, attack symptoms, anatomical location of swelling (if applicable), severity, treatment(s) administered and times of administration, and whether additional medical care was sought for the attack. Subjects will complete the diaries from enrollment through the end of Part 2 (ie, Week 48).

The P/C will be instructed to bring the subject's diary with them to each study visit. Diaries will be collected at each visit through Week 48, and new diaries will be dispensed at each visit prior to Week 48.

Subjects who withdraw from the study should continue to record the occurrence of HAE attacks in their diary until they return to the site for the appropriate EOS visit.

Once a subject completes or discontinues the study, the site must collect all diaries from the P/C. Study staff are not permitted to make any entries into the diary.

11. ADVERSE EVENT MANAGEMENT AND REPORTING

11.1. Adverse Events

11.1.1. Definitions

11.1.1.1. Adverse Event

An AE is any untoward medical occurrence in a clinical study subject. No causal relationship with the study drug/IMP or with the clinical study itself is implied. An AE may be an unfavorable and unintended sign, symptom, syndrome, or illness that develops or worsens during the clinical study. Clinically significant results of diagnostic procedures including abnormal laboratory findings (eg, requiring unscheduled diagnostic procedures or treatment measures, or resulting in withdrawal from the study) are considered to be AEs. If the diagnostic procedure prompts no additional treatment, visits, or monitoring, it will not meet the definition of an AE.

AEs include the following:

- AEs not previously observed in the subject that emerge during the protocol-specified AE reporting period (see Section 11.1.1.4).
- Findings from protocol-mandated interventions. This can include laboratory assessments performed in the clinical study. AEs should be reported only if the abnormalities are adverse changes from baseline and clinically significant as described above.
- Pre-existing medical conditions (other than HAE) judged by the investigator to have worsened in severity or frequency or undergone an adverse change in character during the protocol-specified AE reporting period. When recording such events on an AE/SAE CRF page, it is important to convey the concept that the preexisting condition has adversely changed by including applicable descriptors (eg, “more frequent headaches” or “worsened headache”).
- Untoward and unintended responses resulting from medication errors and uses outside what is foreseen in the protocol, including misuse and abuse of the product, should be reported as an AE.

Surgical procedures should not be reported as AEs. The condition for which the surgery is required should be reported as an AE if it occurs or is detected during the study period. Planned surgical measures permitted by the clinical study protocol and the condition(s) leading to these measures are not AEs if the condition(s) was (were) known before the start of study treatment. In the latter case, the condition should be reported as medical history.

For the purposes of this protocol, HAE attacks and their associated symptoms will not be defined as AEs, even if the subject requires hospitalization. HAE attacks and associated symptoms are reported in the subject’s diary and are a reflection of the disease under study. Events that trigger an HAE attack and meet the definition of an AE, such as an infection or trauma, should be reported as AEs.

AEs are designated as “nonserious” or “serious”.

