4.4.5. Berotralstat Risk Analysis

Potential risks and findings from nonclinical and clinical studies of berotralstat are discussed in Section 6 of the IB (Summary of Data and Guidance for the Investigators). Adverse reactions seen during clinical trials with berotralstat at 150 mg once daily (QD) include abdominal pain, vomiting, diarrhea, and gastroesophageal reflux disease. In the prescribing information, a warning and precaution is noted for an increase in QT prolongation which can occur at dosages higher than the recommended adolescent and adult dose of 150 mg QD.

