6.7.7.2. Adjusted Attack

Subject-reported attacks reported must meet the following criteria (applied in order) for inclusion in effectiveness analyses:

- Attack must include at least 1 symptom of swelling;
- Subject response to diary question, “In retrospect, could there be an alternative explanation for your symptoms other than an HAE attack (ie, allergic reaction, viral cold etc.)?” must be “no”.
- Attack must be unique (attack began > 24 hours from the end of the prior attack);
- Any attack that begins within 24 hours from the end of a prior attack will be combined with the prior attack;

- If the entire adjusted attack is untreated, it must have a duration > 24 hours.

Using the above criteria, adjusted attacks will be determined programmatically. For adjusted attacks that span 2 or more subject-reported attacks, attack triggers, locations, symptoms, duration, and other characteristics will be based on the information from each component subject-reported attack. Additionally, the start date/time of the adjusted attack will be the start date/time from the first attack and then end date/time of the adjusted attack will be the end date/time from the last attack being collapsed programmatically.

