6.7.7.9. Attack Location

The anatomical location of each subject-reported and adjusted attack will be determined based on the symptoms indicated in the diary as shown in Table 3.

Table 3: Determination of Attack Location Using Symptoms Collected in the Diary

Abdominal-Only Attack	Mixed Attack	Non-abdominal Attack (Inclusive of Skin and Airway Swelling)

Symptoms checked must only come from this box:
 
Internal swelling or symptoms of internal swelling in the abdomen:
 
 Nausea Abdominal discomfort Cramps (colicky pain) Vomiting Abdominal pain Diarrhea 	
Must have at least 1 symptom from left and right box (from abdominal and non-abdominal attack characterization)
	
Symptoms checked must only come from this box:
 
Peripheral (Non-laryngeal) Events:
 
Visible swelling:
 
 face/head neck (outer swelling) legs buttocks/genitals eyes arms feet stomach (outside) hands chest/back joints

Abdominal-Only Attack	Mixed Attack	Non-abdominal Attack (Inclusive of Skin and Airway Swelling)
		
Pink rings (erythema marginatum) with other swelling
 
Laryngeal Events:
 
Internal swelling or symptoms of internal swelling of the airways:
 
 mouth/tongue/lips lump in throat/tightness change in voice difficulty swallowing difficulty breathing

Note: Symptoms of headache and substantial fatigue may be checked by the subject but play no role in the characterization of the location of a subject-reported attack.

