8.5.7. Incomplete Date and Time for a Subject-Reported Attack

For HAE attacks reported with a missing start/stop date and or time, the following algorithm will be applied:

- Missing start time but start date present:

The start time will be set to 12:00PM.

- Missing start date and time:

The start date will be set to the diary date for which the question was answered “Yes”.
The start time will be set to 12:00PM.

- Missing stop time, but stop date present:

The stop time will be set to 11:59PM.

- Missing stop date and time:

The stop date will be set to the attack start date, and the stop time will be set to 11:59PM.

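### No step requires diary entries that the SAP removes as attacks to be assessed as possible adverse events, so a gastrointestinal drug reaction logged as a suspected attack can miss every TEAE table and every adjusted-attack table

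*Protocol*

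**What the plan says.** Protocol 4.4.5 says that adverse reactions seen at 150 mg once daily "include abdominal pain, vomiting, diarrhea, and gastroesophageal reflux disease". SAP 6.7.7.9 (Table 3) classifies an attack as abdominal-only when all its symptoms come from a box headed "Internal swelling or symptoms of internal swelling in the abdomen". That box holds nausea, abdominal discomfort, cramps, vomiting, abdominal pain and diarrhea.

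The diary belongs to the parent or caregiver. Protocol 10.11 says: "The P/C will fill out the HAE attack diary whenever an attack (or suspected attack) occurs". Protocol 11.1.1.1 then separates attacks from safety reporting: "HAE attacks and their associated symptoms will not be defined as AEs, even if the subject requires hospitalization".

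SAP 6.7.7.2 filters the diary entries, which "must meet the following criteria (applied in order) for inclusion in effectiveness analyses". Three of the criteria matter here. The entry must include a symptom of swelling. The answer to the diary question "could there be an alternative explanation for your symptoms other than an HAE attack" must be no. And "If the entire adjusted attack is untreated, it must have a duration > 24 hours". Episodes that start within 24 hours of the end of an earlier one are merged with it. For a missing stop date and time, SAP 8.5.7 says: "The stop date will be set to the attack start date, and the stop time will be set to 11:59PM".

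**The concern.** Two classifications of the same episode are made at different times by different parties, and nothing connects them. During the study, the site may follow the protocol by treating a logged bout of vomiting or diarrhea as attack symptoms and recording no adverse event. At analysis, the SAP program may rule that the same bout was not an attack. If so, the reason for leaving it out of adverse events has gone, but no adverse event record exists, and the analyst cannot create one afterwards.

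Safety and tolerability is a secondary objective, gastrointestinal reactions are the ones the protocol itself names, and about 30 children are planned. A few events classified this way could change the gastrointestinal profile that is reported.

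**Working it through.** **Symptom overlap.** Named reactions (Protocol 4.4.5): abdominal pain, vomiting, diarrhea, gastroesophageal reflux disease. Abdominal-attack symptoms (SAP Table 3): the six listed above. Common to both: abdominal pain, vomiting, diarrhea, so 3 of 4. Reflux is not on the attack list.

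**Trace of one entry.** Take an entry with gastrointestinal symptoms only, logged as a suspected attack and not also recorded as an adverse event.

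| Entry | Adjusted attack? | TEAE? |
|---|---|---|
| (a) another explanation possible: yes | No | No |
| (b) answer no, untreated, 24 h or less, not merged with another episode | No | No |
| (c) answer no, and treated or longer than 24 h | Yes, if the swelling criterion is met | No |

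Row (c) depends on whether Table 3's abdominal symptoms count as swelling. The box heading suggests that they do, but SAP 6.7.7.2 does not say so. If they do not, gastrointestinal-only entries fail at the first criterion whatever their duration or treatment, and the gap is wider.

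**Missing stop date and time.** With the start time also missing, SAP 8.5.7 sets the start to 12:00PM and the stop to 11:59PM the same day: 11 h 59 min = 11.98 h. With a recorded start, the longest possible duration is midnight to 11:59PM: 23 h 59 min = 23.98 h. Both are below 24 h, so an untreated entry with no stop date and time always falls in row (b) unless it is merged with another episode.

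**Where rows (a) and (b) still appear.** SAP 6.7.7.1 counts every entry on the attack page as a subject-reported attack. SAP 6.7.7.4 computes rates of these through Weeks 12 and 48. SAP 12.1.1, 12.1.2 and 12.1.4 summarize their number, symptom days and characteristics. Table 7 plots their rate (figures 14.2.5.4 to 14.2.5.6) and lists the diary (16.2.6.1.1). Table 7's numbered tables for attack rate, duration, characteristics, location and symptom days are titled for adjusted attacks only.

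**Search for a return path.** Protocol 8.3.2 asks sites to query how the drug is taken once a gastrointestinal symptom has already been noted as an adverse event. The diary footnote to the Schedule of Assessments (Protocol Table 2) covers problems with entries, which the subject or parent corrects. Neither calls for an adverse event assessment of a diary entry.

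**Scale, for illustration only.** The plan's one relevant figure is the chance of seeing at least one TEAE with a 10% rate in 30 subjects (Protocol 12.1): 1 − 0.9^30 = 0.9576, which reproduces the stated 96%. If a share m of affected children have the reaction recorded only as an attack, the chance becomes 1 − [1 − 0.10 × (1 − m)]^30.

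| m (assumed) | Chance of at least one TEAE |
|---|---|
| 0 | 95.8% |
| 10% | 94.1% |
| 25% | 90.4% |
| 50% | 78.5% |
| 75% | 53.2% |

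The documents give no value for m. The table shows sensitivity and is not an estimate.

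**The case against.** A reader might infer that such an event reaches no effectiveness table at all. The documents do not support that: it remains a subject-reported attack and enters the summaries and figures listed above. What stands is narrower. Wherever it appears, it is counted as disease and not as tolerability.

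A reader might also infer that the protocol forbids recording the event as an adverse event. It does not. The exclusion covers HAE attacks, not everything a parent writes in the diary, and a drug-caused event that is not an attack still meets the general definition in Protocol 11.1.1.1. Adverse events are asked about at contacts (Protocol 9.2.2 and 9.4.1), the investigator is expected to seek a diagnosis (Protocol 11.1.2), and diaries are reviewed with the parent. An event is lost only if the parent mislabels it, does not mention it when asked, and the site does not reclassify it. This is a fair limit on the point. But reclassification is permitted and not required, so capture depends on each site's practice.

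Three further inferences go too far. A numerical bias cannot be stated without a mislabelling rate. A larger loss on berotralstat than during standard of care is plausible, since that period is meant as a safety control (Protocol 4.4.4), but no document establishes it, and Protocol 11.1.1.5 also requires causality assessment for standard-of-care HAE medication. Whether the data monitoring committee's data share the gap depends on its charter, which is a separate document. The CRF completion guidelines, also separate, may already address reconciliation.

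**Conclusion.** The point holds as a missing reconciliation step. On the text of the protocol and SAP, a gastrointestinal drug reaction logged as a suspected attack can be absent from every TEAE table and every adjusted-attack table. The clearest case is an entry for which the family has said that another explanation is possible: the data themselves question the attack label, yet the only planned consequence is removal from adjusted attacks.

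The likely direction is under-counting of gastrointestinal TEAEs while the diary runs on treatment, Day 1 to Week 48. The size is unknown. The conclusion assumes that some parents log drug reactions as suspected attacks and that some sites do not record them separately. This is a cheap improvement, not a flaw that undermines the study.

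**What to change.** 1. **Protocol 11.1.1.1 and 10.11.** At the existing diary review, the investigator assesses each entry for which another explanation was said to be possible, and each abdominal-only entry that is untreated and lasts 24 hours or less (including entries that the imputation rule would put there). If the episode is judged not to be an HAE attack, it is recorded as an adverse event. Entries judged to be attacks stay out of adverse events. Recording every unconfirmed abdominal episode as an adverse event would go too far, because it would turn real attacks into TEAEs.

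2. **SAP 11.1 and Table 7.** Add a table of abdominal subject-reported attacks that are excluded from adjusted attacks, by reason for exclusion and by symptom, for the standard-of-care period, Weeks 1–12 and Weeks 1–48, placed beside the gastrointestinal TEAEs. This uses only data already collected, and shows the reader how much could be at issue even where step 1 was not applied.

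The cost is a small added task for sites and one table. The gastrointestinal TEAE rate may become slightly less favourable, and there is some risk that a true mild attack is recorded as an adverse event.
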